
 To compare daprodustat to placebo on measures of iron status, rhEPO and Transfusion use 	
 Observed and change from baseline in hepcidin, ferritin, transferrin saturation, serum iron, total iron binding capacity (TIBC) Average monthly oral iron dose/participant (mg) to Week 28 N (%) of participants who reduced oral iron supplementation from baseline N (%) of participants requiring IV iron each month. Average monthly IV iron dose/participant (mg) to Week 28 Time to first IV iron, rhEPO and Transfusion use

Objectives	Endpoints
	
 Summary of frequency and dose of IV iron

 To compare daprodustat to placebo on renal function 	
 Estimated Glomerular Filtration Rate (eGFR) observed and change from baseline Serum creatinine observed and change from baseline N (%) transitioning to dialysis

 Evaluate the dose adjustment schemes 	
 Assigned dose by visit Most recent dose prior to Week 24, Week 28 and End of Treatment Maximum achieved dose Number (%) of participants with 0, 1, 2 or >2 dose adjustment Mean number of dose adjustments Time dose held for Hgb\geq13 g/dL

 To compare daprodustat to placebo on BP medication changes 	
 N (%) of subjects who had no change, an increase or a decrease in the number of BP medications from baseline to week 28 or final visit for non-completers

 To compare daprodustat to placebo on the severity and change in symptoms 	
 N(%) of participants within each PGI-C symptom change.

 To compare daprodustat to placebo for improving physical activity (actigraphy) 	
 Change in percent and mean number of hours of daily activity from baseline. Change in percent sleep efficiency from baseline.

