7.7.2. Rescue Criteria

A rescue algorithm is provided to minimize participants having an inadequate response to the treatment for their anemia for an extended period of time and to enable consistency in the application of rescue therapy across the study. Details are provided in [Table 7](#).

This rescue algorithm **does not** apply to participants with low Hgb as a result of an acute or subacute event with an identifiable cause (e.g., GI bleed, blood loss due to surgery or vascular access). In these cases, treatment should be directed to the specific cause and randomized treatment will be continued at the current dose (unless Hgb is ≥ 13 g/dL which requires a dose hold).

Table 7 Rescue Algorithm for Anemia Management

Evaluate Participant for Rescue starting from Week 4 if:	

 • HemoCue Hgb is <7.5g/dL, or • HemoCue Hgb is <8.5g/dL and participant is symptomatic¹, or • HemoCue Hgb is <8.5 g/dL on three consecutive visits 	
Step 1: Initial Intervention	
Initial intervention depends on the participant's iron status:
 
 • If participant has TSAT < 15% and/or Ferritin < 50 ng/mL from a prior study visit, then 
 ○ continue with study treatment, and ○ intervene with iron therapy: Single dose of IV iron up to 1000 mg (in addition to the iron management criteria) 
At the next study visit in 4 ±1 weeks, recheck HemoCue Hgb. If HemoCue Hgb value continues to meet the evaluation criteria for rescue, then Proceed to Step 2.
 
 • If participant has TSAT ≥15% and Ferritin ≥ 50ng/mL, proceed to step 2.
Step 2: Rescue	
Randomized treatment should be permanently discontinued (but participant should remain in study to monitor Hgb) and the participant should be rescued according to local clinical practice:
 
 • If HemoCue Hgb remains <8.5 g/dL despite Initial Intervention (Step 1) based on the average of two HemoCue Hgb values ² • Rescue can be considered IV iron, rhEPOs and/or Transfusions.

1. Symptoms should be related to anemia of CKD. Further information regarding collecting this data will be stated in the SRM.

2. Repeat HemoCue Hgb at the same study visit to confirm Hgb (using the same sample); take average of 2 values.

The study site will supply any rescue medication that will be obtained locally.

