- Time to first IV iron use, rhEPO and transfusion use is defined as the time from Randomization until the date on which a participant received IV iron, rhEPO, or transfusion use for the first time after Randomization. Time to first IV iron use will use on-treatment values only, while time to first rhEPO and transfusion use will use both on-treatment and on/off-treatment values post-randomization. First rhEPO use differs from rescue, there may be instances of rhEPO being given but participants not rescued. The Number (%) of participant received IV iron, rhEPO and transfusion use within each treatment arm will be summarised with mean, standard deviation, minimum, P25, median, P75, and maximum of the time to first IV, rhEPO and transfusion use by treatment group.
- The frequency and dose of IV iron use, rhEPO and transfusion use will be summarized using mean, standard deviation, minimum, P25, median, P75, and maximum by treatment group.
- A listing of all IV iron use, rhEPO and transfusion use during the study will be provided. This listing will include treatment, site ID, unique subject ID, select demographic information, frequency and dose of IV iron use, frequency and dose of rhEPO use, and frequency of transfusions.

Renal Function

| Endpoint / Variables |
|---|
| 
 • Estimated Glomerular Filtration Rate (eGFR) observed and change from baseline • Serum creatinine observed and change from baseline • N (%) transitioning to dialysis |
| Planned Exploratory Displays |
| 
 • eGFR and serum creatinine on-treatment values will be summarized using mean, standard deviation, minimum, P25, median, P75, and maximum for each scheduled visit by treatment group. Graphical summaries will be provided. • Change from baseline in eGFR and serum creatinine on-treatment values will be summarized using mean, standard deviation, minimum, P25, median, P75, and maximum for each scheduled visit by treatment group and by subgroup ADPKD. Graphical summaries will be provided. • Number (%) of participants transitioning to dialysis will be summarized by treatment group. |

CONFIDENTIAL

205270

Dose Adjustment Scheme

| Endpoint / Variables |
|---|

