| 2.94. | ITT | EFF_T17 | Summary of On-Treatment Transferrin Saturation (%) by Visit | On-Treatment | DR, SAC |
| 2.95. | ITT | EFF_T18 | Summary of On-Treatment Transferrin Saturation (%) Change from Baseline by Visit | On-Treatment | DR, SAC |
| 2.96. | ITT | EFF_T17 | Summary of On-Treatment Ferritin (ug/L) by Visit | On-Treatment For min, max, median, p25 and p75, you do not need to summarize with log transformed data since $aval = \exp(\log(aval))$ | DR, SAC |
| 2.97. | ITT | Safety, Shell 27 | Summary of On-Treatment Ferritin (ug/L) Percent Change from Baseline by Visit | On-Treatment | DR, SAC |
| 2.98. | ITT | EFF_T17 | Summary of On-Treatment Serum Iron (umol/L) by Visit | On-Treatment For min, max, median, p25 and p75, you do not need to summarize with log transformed data since $aval = \exp(\log(aval))$ | DR, SAC |
| 2.99. | ITT | Safety, Shell 27 | Summary of On-Treatment Serum Iron (umol/L) Percent Change from Baseline by Visit | On-Treatment | DR, SAC |
| 2.100. | ITT | EFF_T17 | Summary of On-Treatment Total Iron Binding Capacity (umol/L) by Visit | On-Treatment | DR, SAC |
| 2.101. | ITT | EFF_T18 | Summary of On-Treatment Total Iron Binding Capacity (umol/L) Change from Baseline by Visit | On-Treatment | DR, SAC |
| 2.102. | ITT | EFF_T32 | Summary of On-Treatment Average Monthly Oral Elemental Iron Dose (mg) to Week 28 | On-Treatment | DR, SAC |

CONFIDENTIAL

205270

| Efficacy: Tables | | | | | |
|--|-------------------|-----------------------------|---|---|--------------------|
| No. | Population | IDSL / Example Shell | Title | Programming Notes | Deliverable |
| 2.103. | ITT | EFF_T33 | Summary of On-Treatment Number of Subjects who reduced oral elemental iron supplementation relative to baseline during EP | On-Treatment | DR, SAC |
| 2.104. | ITT | EFF_T33 | Summary of On-Treatment Number of Subjects who reduced oral elemental iron supplementation relative to baseline during treatment period | On-Treatment | DR, SAC |
| 2.105. | ITT | EFF_T32 | Summary of On-Treatment Average monthly IV iron dose/subject (mg) to Week 28 | On-Treatment | DR, SAC |
| 2.106. | ITT | EFF_T29 | Summary of Time to First IV Iron Use While On-Treatment | On treatment only | DR, SAC |
| 2.107. | ITT | EFF_T29 | Summary of Time to First rhEPO Use | Page by on/off trt & on trt | DR, SAC |
| 2.108. | ITT | EFF_T29 | Summary of Time to First Transfusion Use | Page by on/off trt & on trt | DR, SAC |

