| 2.109. | ITT | EFF_T44 | Summary of frequency and dose of IV iron use While On-Treatment | By treatment and by baseline iron usage | DR, SAC |
| 2.110. | ITT | EFF_T44 | Summary of frequency and dose of rhEPO use Post-Randomization | By treatment and by baseline iron usage | DR, SAC |
| 2.111. | ITT | EFF_T44 | Summary of frequency and dose of transfusion use Post-Randomization | By treatment and by baseline iron usage | DR, SAC |
| Exploratory Efficacy Statistical Analyses: Renal Function | | | | | |
| 2.112. | ITT | EFF_T17 | Summary of On-Treatment eGFR by Visit | On-Treatment | DR, SAC |
| 2.113. | ITT | EFF_T18 | Summary of On-Treatment eGFR Change from Baseline by Visit | On-Treatment | DR, SAC |
| 2.114. | ITT | EFF_T17 | Summary of On-Treatment eGFR by Visit, sub-group ADPKD | On-Treatment By ADPKD and treatment | DR, SAC |

CONFIDENTIAL

205270

| Efficacy: Tables | | | | | |
|--|-------------------|-----------------------------|--|--|--------------------|
| No. | Population | IDSL / Example Shell | Title | Programming Notes | Deliverable |
| 2.115. | ITT | EFF_T18 | Summary of On-Treatment eGFR Change from Baseline by Visit, sub-group ADPKD | On-Treatment By ADPKD and treatment | DR, SAC |
| 2.116. | ITT | EFF_T17 | Summary of On-Treatment Serum creatinine by Visit | On-Treatment | DR, SAC |
| 2.117. | ITT | EFF_T18 | Summary of On-Treatment Serum creatinine Change from Baseline by Visit | On-Treatment | DR, SAC |
| 2.118. | ITT | EFF_T39 | Summary of Number transitioning to dialysis | | DR, SAC |
| Exploratory Efficacy Statistical Analyses: Dose Adjustment Scheme | | | | | |
| 2.119. | ITT | EFF_T45 | Summary of Assigned Dose (mg) by Visit | | DR, SAC |
| 2.120. | ITT | EFF_T50 | Summary of Categories of Assigned Dose by Visit for Daprodustat | | DR, SAC |
| 2.121. | ITT | EFF_T46 | Summary of Most recent dose prior to Week 24, Week 28 and end of study treatment | | DR, SAC |
| 2.122. | ITT | EFF_T39 | Summary of Maximum achieved dose | | DR, SAC |
| 2.123. | ITT | EFF_T47 | Summary of Number of Subjects with 0, 1, 2, or >2 dose adjustments during the treatment period | | DR, SAC |
| 2.124. | ITT | EFF_T48 | Summary of Mean and median number of dose adjustments during the treatment period | | DR, SAC |
| 2.125. | ITT | EFF_T49 | Summary of Time dose held for Hemoglobin ≥ 13 g/dL during the treatment period | | DR, SAC |

CONFIDENTIAL

205270

| Efficacy: Tables | | | | | |
|---|------------|----------------------|--|--|-------------|

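### IV iron displays stop at treatment discontinuation while rhEPO and transfusion displays continue, so IV iron rescue after the stop is left out of the IV iron summaries

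*SAP*

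**What the plan says.** Protocol Section 4 lists one exploratory endpoint for the three therapies, with no restriction by treatment status: "Time to first IV iron, rhEPO and Transfusion use".

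Protocol 7.7.2, Table 7, has two steps that can involve IV iron:

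- **Step 1** (TSAT below 15% and/or ferritin below 50 ng/mL). Study treatment continues, and the instruction is to "intervene with iron therapy: Single dose of IV iron up to 1000 mg".
- **Step 2.** "Randomized treatment should be permanently discontinued (but participant should remain in study to monitor Hgb"). The same step says "Rescue can be considered IV iron, rhEPOs and/or Transfusions". Participants who meet both the TSAT and ferritin thresholds go straight to this step.

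SAP 7.4.2 (Iron Parameters) defines time to first use as running from randomization to the first use after randomization. It then splits the three therapies: "Time to first IV iron use will use on-treatment values only, while time to first rhEPO and transfusion use will use both on-treatment". For the latter two, off-treatment use is included as well. The N (%) needing IV iron is limited to the period of study treatment.

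The display list in SAP 10.10.6 follows the split:

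- Table 2.106: "Summary of Time to First IV Iron Use While On-Treatment". Tables 2.107 (rhEPO) and 2.108 (transfusion) are each paged both on/off treatment and on treatment.
- Table 2.109: "Summary of frequency and dose of IV iron use While On-Treatment". Table 2.110: "Summary of frequency and dose of rhEPO use Post-Randomization". Table 2.111 treats transfusion as 2.110 treats rhEPO.

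SAP Table 1, which lists changes from the protocol, has a row extending the IV iron frequency and dose summary to rhEPO and transfusion. It does not mention the on-treatment limit on IV iron and gives no reason for it.

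**The concern.** The counting window for IV iron closes at the event that makes IV iron a permitted rescue. A participant rescued with rhEPO after the stop is counted as an rhEPO user. A participant whose first IV iron is a post-stop rescue is counted as a non-user of IV iron. If one arm has more rescue stops, its IV iron use is understated by more, and the between-arm contrast moves.

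Outside intolerance to oral iron, protocol 7.7.1 reserves IV iron for participants being evaluated for rescue, so the use that is cut off is not incidental to the endpoint.

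**Working it through.** The documents state no rescue rate, no IV iron use rate and no share of rescues treated with IV iron, so there is no figure of the plan's own to reproduce. The check has two parts.

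**1. Which IV iron is lost**

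- *Boundary.* On-treatment ends one day after the treatment stop date for iron and transfusion data (SAP 10.4.1.1), and one day after the last non-zero dose for concomitant medication records (SAP 10.4.1.3). IV iron up to that day is counted.
- *Step 1 IV iron.* Given while study treatment continues, so it is counted.
- *Step 2 IV iron after earlier on-treatment IV iron.* The participant is already a user with a first-use date. Only the later doses are lost, from Table 2.109.
- *Step 2 IV iron with no earlier on-treatment IV iron.* The participant is lost as a user, has no first-use time, and contributes no dose. These are mainly participants with TSAT of at least 15% and ferritin of at least 50 ng/mL who skip Step 1. Protocol 6.2 excludes lower values at screening, so this route is open to anyone who stays above the thresholds.
- *Where the lost records still appear.* Listing 30 (all IV iron, rescue, rhEPO and transfusion), and Table 1.17 (post-treatment medications by ATC level and ingredient). Table 1.17 gives no route, timing or dose. The rescue summaries (Tables 2.41 and 2.42; SAP 7.3.2.1) are specified by reason, algorithm step and time to stop, not by rescue agent.

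**2. How far the contrast could move (illustration only)**

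Inputs:

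- N = 300 per arm (protocol 10.2.1).
- b = on-treatment IV iron users, assumed 5% in both arms, so the SAP display shows a difference of 0.0 points.
- r = proportion with a rescue stop (assumed).
- s = proportion of rescue stops whose first IV iron falls after the boundary (assumed 10% to 50%, equal in both arms).

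Formulas:

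- Users missed per arm = N × r × s
- Users counted to Week 28 = b + r × s
- Shift in the difference = (r placebo − r daprodustat) × s; b cancels.

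| r placebo / daprodustat | Missed, placebo | Missed, daprodustat | All use, placebo | All use, daprodustat | Difference (points) |
|---|---|---|---|---|---|
| 5% / 5% | 1.5 to 7.5 | 1.5 to 7.5 | 5.5% to 7.5% | 5.5% to 7.5% | 0.0 |
| 10% / 3% | 3 to 15 | 0.9 to 4.5 | 6.0% to 10.0% | 5.3% to 6.5% | 0.7 to 3.5 |
| 15% / 3% | 4.5 to 22.5 | 0.9 to 4.5 | 6.5% to 12.5% | 5.3% to 6.5% | 1.2 to 6.0 |
| 20% / 5% | 6 to 30 | 1.5 to 7.5 | 7.0% to 15.0% | 5.5% to 7.5% | 1.5 to 7.5 |

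For example, with 20% v 5% and s = 50%: (0.20 − 0.05) × 0.50 = 0.075, or 7.5 points. With equal r and s the shift is zero.

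**The case against.** The on-treatment rule can be defended. The iron management criteria in protocol 7.7.1 are written for participants receiving study treatment, and after Step 2 rescue follows local practice. The oral iron doses, iron laboratory values and average monthly IV iron dose in SAP 7.4.2 are also on treatment. On-treatment IV iron therefore describes use under the protocol's own rules. That supports keeping the on-treatment version. It does not explain why rhEPO and transfusion, which become rescues at the same step, also get a post-randomization version and IV iron does not.

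A reader might draw four stronger conclusions that the documents do not support:

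- *That no table counts post-stop IV iron.* Table 1.17 does, by ingredient. It cannot stand in for Tables 2.106 or 2.109, but the use is not confined to a listing.
- *That anyone rescued with IV iron counts as a non-user.* Step 1 recipients are already users. Multiplying the rescue rate by the share of rescues given IV iron therefore overcounts the missed users.
- *That the three therapies cannot be compared.* Tables 2.107 and 2.108 have on-treatment pages, so time to first use can be compared on that basis. Only frequency and dose (2.109 against 2.110 and 2.111) lack a common basis.
- *That the bias is known to be large, and in a known direction.* No rescue rate is given, and protocol 5.4 expects few drop-outs for lack of effect.

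**Conclusion.** The asymmetry is real, is not listed as a change from the protocol, and is not explained. IV iron first given more than one day after the stop, and all post-stop doses, are absent from the IV iron displays, while the corresponding rhEPO and transfusion use is tabulated.

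The size is unknown. The range of 0 to about 7.5 percentage points rests entirely on assumed rescue rates (5% to 20% on placebo, 3% to 5% on daprodustat) and an assumed share of 10% to 50%, taken as equal in both arms. More generally the shift is the difference between arms in r × s, and it vanishes when those products are equal. If placebo is rescued more, with a similar s, the rule hides placebo IV iron use and works against daprodustat on this contrast.

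The endpoint is exploratory and SAP 7.4 plans no testing of it, so no primary, principal secondary or safety conclusion depends on this point. It is worth correcting because the displays leave out one of the three named rescues at the moment it is used.

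**What to change.** Page Table 2.106, Table 2.109 and the N (%) IV iron display for all post-randomization use to Week 28 as well as on treatment, as Tables 2.107 and 2.108 already are. Leave the average monthly IV iron dose as it is: it divides on-treatment dose by on-treatment time and is a coherent on-treatment rate.

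The cost is a few repeated pages from existing shells. No new data are needed: protocol 7.7.2 already requires the rescue drug, its date and its dosage regimen in the eCRF, and protocol Table 3 continues rescue medication recording after treatment discontinuation.

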7.4. Exploratory Efficacy Analyses

No statistical testing is planned for exploratory endpoints.

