| 
 • Hepcidin, ferritin, and serum iron on-treatment values will be log-transformed (see Section 5.2.2) and summarized using geometric mean, coefficient of variation, minimum, P25, median, P75, and maximum for each scheduled visit by treatment group. Graphical summaries will be provided. • TSAT and TIBC on-treatment values will be summarized using mean, standard deviation, minimum, P25, median, P75, and maximum for each scheduled visit by treatment group. Graphical summaries will be provided. • Percent change from baseline in log-transformed (see Section 5.2.2) hepcidin, ferritin, and serum iron on-treatment values will be summarized using geometric mean, coefficient of variation, minimum, P25, median, P75, and maximum for each scheduled visit by treatment group. Graphical summaries will be provided. • Change from baseline in TSAT and TIBC on-treatment values will be summarized using mean, standard deviation, minimum, P25, median, P75, and maximum for each scheduled visit by treatment group. Graphical summaries will be provided. • Average monthly oral or IV iron dose (mg)/participant to Week 28 will be determined by calculating the total elemental oral or IV iron dose per participant from Day 1 to Week 28 while the participant was on randomized treatment and dividing by (the number of days the participant was on randomized treatment/30.4375 days). (see Section 10.6.3) • Average monthly oral iron dose/participant and average monthly IV iron dose/participant at baseline, and while on treatment to Week 28 will be summarized by treatment group (see Section 10.6.3). Summaries will include mean, standard deviation, minimum, P25, median, |

CONFIDENTIAL

205270

P75, and maximum by treatment group.

- The number and percentage of participants that reduced oral iron supplementation relative to baseline during the EP and during the treatment period while on treatment will be summarized by treatment group (see Section 10.6.3).
- The number and percentage of participants who required IV iron during study treatment (day 1 to week 28) will be summarized by treatment group.

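### Timing statistics for first IV iron, rhEPO and transfusion use cover recipients only and ignore censoring, so they cannot be compared between arms

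*SAP*

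**What the plan says.** Protocol Section 4 lists "Time to first IV iron, rhEPO and Transfusion use" under an exploratory objective to compare daprodustat with placebo.

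SAP 7.4.2 (Iron Parameters) states that the time is "defined as the time from Randomization until the date on which a participant received IV iron, rhEPO, or transfusion use"; only the earliest receipt following randomization counts. One sentence then plans two things by arm. It opens with "The Number (%) of participant received IV iron, rhEPO and transfusion use within each treatment arm" and continues that these "will be summarised with mean, standard deviation, minimum, P25, median, P75, and maximum of the time to first IV, rhEPO and transfusion use".

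The observation windows differ. For IV iron, "Time to first IV iron use will use on-treatment values only". For the other two, "time to first rhEPO and transfusion use will use both on-treatment and on/off-treatment values post-randomization". The displays are Tables 2.106 (IV iron, on-treatment), 2.107 (rhEPO) and 2.108 (transfusion), the last two paged by on-treatment and by on/off-treatment.

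Need is also displayed elsewhere. In 7.4.2, "The number and percentage of participants who required IV iron during study treatment (day 1 to week 28) will be summarized by treatment group", and Tables 2.109 to 2.111 give frequency and dose.

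Neither 7.4.2 nor 10.6.3 gives a censoring rule, Kaplan-Meier estimate or rate for these times. Time to rescue, a secondary endpoint, has an event date, a censored time, person-years and a Cox model (SAP 7.3.2.1 and 10.6.3). SAP 7.4 states: "No statistical testing is planned for exploratory endpoints".

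**The concern.** These are time-to-event endpoints that some participants, perhaps most, will never reach. The definition gives a non-recipient no value, and nothing in the visible text assigns one. The mean, SD, median, quartiles and range are therefore all conditional on having had the event. An arm in which few need the therapy and an arm in which many do can show nearly the same average time to first use. A reader using these columns for the stated comparison could conclude that timing was alike, or even earlier in the arm with less need.

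The on-treatment pages have a second difficulty. Meeting the rescue criteria leads to permanent discontinuation (Protocol 7.7.2 and 8.1), and rescue may itself consist of IV iron, rhEPO or transfusion. If one arm discontinues more, its on-treatment window is shorter on average. Later first uses in that arm then drop out of both the count and the times.

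The rescue analysis does not fill the gap. The SAP itself notes that rhEPO can be given without the participant being rescued.

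**Working it through.** The documents state no figure for these endpoints, so there is nothing to reproduce. Two illustrations follow. From the documents: 28 weeks of treatment (Protocol 5.4) and 300 randomized per arm (Protocol 10.2.1). All proportions and the constant hazards are assumptions.

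**1. Recipients' times against a censoring-aware contrast**

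Let p be the proportion with first use by τ = 28 weeks.
- Hazard: λ = −ln(1−p)/τ
- Mean among recipients: 1/λ − τ(1−p)/p
- Median among recipients: −ln(1−p/2)/λ
- Restricted mean over all participants: (1−e^(−λτ))/λ = p/λ

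For p = 5%: λ = 0.00183, and the recipients' mean is 545.88 − 532 = 13.88 weeks. For p = 20%: λ = 0.00797, and it is 125.48 − 112 = 13.48 weeks. The hazard ratio is ln(0.95)/ln(0.80) = 0.23.

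| Use by Week 28 | Recipients' mean (weeks) | Difference | Recipients' median (weeks) | Hazard ratio | Restricted mean (weeks) |
|---|---|---|---|---|---|
| 5% v 10% | 13.88 v 13.75 | 0.13 | 13.82 v 13.63 | 0.49 | 27.29 v 26.58 |
| 5% v 20% | 13.88 v 13.48 | 0.40 | 13.82 v 13.22 | 0.23 | 27.29 v 25.10 |
| 10% v 30% | 13.75 v 13.17 | 0.58 | 13.63 v 12.76 | 0.295 | 26.58 v 23.55 |
| 10% v 40% | 13.75 v 12.81 | 0.94 | 13.63 v 12.23 | 0.21 | 26.58 v 21.93 |
| 5% v 40% | 13.88 v 12.81 | 1.07 | 13.82 v 12.23 | 0.10 | 27.29 v 21.93 |

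Recipients' means differ by 0.1 to 1.1 weeks while the hazard ratio runs from 0.49 to 0.10. The median behaves much as the mean does.

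In 4,000 simulated trials at 5% v 20%, a t-test on recipients' times was significant in 4.5%. The arm with less need had a recipients' mean no longer than the other's in 43%. At 10% v 40% the figures were 9% and 28%. A chi-squared test on N (%) separated the arms in essentially every trial in both scenarios. Neither test is planned; they only gauge what each statistic can show.

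**2. On-treatment counting when discontinuation differs**

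Give both arms the same first-use hazard (p = 20%, λ = 0.00797). Let a proportion d of one arm discontinue by Week 28, with independent hazard μ = −ln(1−d)/28, and none of the other. With q = (1−p)(1−d):
- On-treatment N (%): λ/(λ+μ) × (1−q)
- Recipients' mean: 1/(λ+μ) − 28q/(1−q)

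| d | On-treatment N (%) | Recipients' mean (weeks) |
|---|---|---|
| 0% | 20.0% | 125.5 − 112.0 = 13.5 |
| 10% | 0.679 × 0.28 = 19.0% | 85.2 − 72.0 = 13.2 |
| 40% | 0.304 × 0.52 = 15.8% | 38.1 − 25.8 = 12.3 |

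With identical underlying need, the arm that discontinues more appears to use less, and sooner.

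**The case against.** The strongest reply is that the sentence also reports the number and percentage of recipients by arm. At 5% v 20%, those are the figures the reader would see. The separate IV iron count, the frequency and dose tables, a participant listing and the Cox analysis of rescue show need again. This stands. A reader might infer that the display as a whole hides a difference in need; the documents do not support that. What remains is that N (%) says nothing about when, and timing is the endpoint.

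A reader might also infer that stopping treatment shortens the recorded IV iron times of rescued placebo participants. That is not accurate. A recorded time is unchanged; uses after the window closes are not counted, which changes who contributes. The initial rescue step also gives IV iron while study treatment continues (Protocol 7.7.2, Table 7), so that route is captured.

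Two further points stand. First, that the statistics cover recipients only is inferred from the definition; the SAP does not say so, and the table shell is not in the text available. Second, these endpoints are descriptive by design, and timing among recipients beside N (%) is an acceptable description if it is labelled as that. It does not deliver the comparison named in the objective.

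**Conclusion.** The point holds for the timing statistics, not for the whole display. They cannot be compared between arms because they condition on having the event and have no censoring rule. Under constant hazards, recipients' means moved by about a week at most while hazard ratios fell as low as 0.10. For post-randomization rhEPO and transfusion, N (%) remains a sound guide to need. For the on-treatment pages N (%) also depends on time on treatment: 20% could read as 15.8% to 19.0% if 10% to 40% of one arm discontinued.

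These sizes rest on assumed proportions, constant hazards and, in the second illustration, discontinuation independent of need. The importance is low: the endpoint is exploratory and untested, and lies outside the testing hierarchy.

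**What to change.** For Tables 2.106 to 2.108, keep N (%) and replace or supplement the timing statistics with cumulative incidence by arm, for example at Weeks 12 and 28. Label any retained mean or median as describing recipients only.

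- **Post-randomization rhEPO and transfusion pages:** follow from randomization to study completion or withdrawal, with death as a competing event. This needs stating, because SAP 10.6.1 counts participants who die on study as completers. The rescue conventions in 10.6.3 end at treatment stop and cannot be carried over unchanged.
- **On-treatment pages, including IV iron:** treat permanent discontinuation and death as competing events, and show the discontinuation curve beside the first-use curve. This does not equalise time on treatment, but it makes the difference visible. If the SAP instead censors at treatment stop + 1 day, it should state that this censoring is informative, because meeting rescue criteria stops treatment.
- **Dates:** SAP 10.7.2.1 sets missing parts of a concomitant medication start date to 01 and January, which can fall before randomization. A rule is needed for such records.

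The cost is minor programming on three exploratory tables, from medication, treatment and disposition dates already collected. No confirmatory conclusion changes.
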